4.1 Overall Design

This phase 3, randomised, assessor-blinded, active-controlled, parallel-group, multi-site, 24-week trial will compare the efficacy, health-related quality of life, and safety of delgocitinib cream 20 mg/g twice-daily with alitretinoin capsules 30 mg (with an option to reduce to 10 mg during trial conduct) once-daily in adult patients with severe CHE.

The trial will be conducted in approximately 80 sites in European countries and Canada.

For each participant, the trial will last at least 25 weeks and up to 33 weeks, including:

- a screening period of 1 to 4 weeks (at least 1 visit)
- a treatment period of 24 weeks (9 visits)
- a safety follow-up period of 2 to 5 weeks (1 visit for all participants 2 weeks after the last IMP dose, plus a pregnancy follow-up visit for WOCBP treated with alitretinoin 5 weeks after the last IMP dose)

Screening: During the screening visit, after checking eligibility criteria, participants will be dispensed with an eDiary and provided training and instructions to complete the eDiary at home. Participants will be asked to start completing the Hand Eczema Symptom Diary[©] (HESD[©], hereafter referred to as HESD) component of eDiary at least 1 week prior to baseline (Day 1), but preferably from the date the participants receive the eDiary.

Treatment period: On Day 1, eligible participants will be randomised in a 1:1 ratio to receive 1 of the following treatments:

- Topical administration of delgocitinib cream 20 mg/g, twice-daily until Week 16, which may continue up to Week 24 depending on clearance status (i.e. IGA-CHE score) and clinical benefit.
- Oral administration of alitretinoin capsules 30 mg (with an option to reduce to 10 mg during trial conduct), once-daily until Week 12, which may continue up to Week 24 depending on clearance status (i.e. IGA-CHE score) and clinical benefit.

Randomisation will be stratified by subtype (hyperkeratotic/non-hyperkeratotic) and region (North America/Europe).

Efficacy (HECSI and IGA-CHE) will be evaluated by an assessor blinded to treatment assignment (hereinafter referred to as 'blinded assessor'). Based on the efficacy assessments, the blinded assessor will make recommendations for the following:

- Treatment discontinuation to initiate rescue medication due to lack of efficacy (Sections 6.8.2 and 7.1).
- To continue, stop or restart treatment from Week 12 and onwards for alitretinoin (Section 6.5.1).

Safety assessments, adverse events, and treatment decisions will be made by the unblinded investigator to allow for:

- Dose reductions for participants treated with alitretinoin (Section 6.5).
- Permanent IMP discontinuation (Section 7.1).
- Decisions to continue, stop or restart the IMP from Week 16 for delgocitinib or Week 12 for alitretinoin (Section 6.5.1).

Participants will stop the IMP if they achieve an IGA-CHE score of 0 (clear) or 1 (almost clear) after 16 weeks of delgocitinib treatment or 12 weeks of alitretinoin treatment. Participants who discontinued delgocitinib treatment due to IGA-CHE score of 0 or 1 must restart treatment if they relapse to an IGA-CHE score of ≥2. These participants will continue attending the treatment period visits as planned until Week 24.

Participants who permanently discontinue the IMP will attend an ET visit, they will stop attending the treatment period visits and will only be asked to return to the trial site at Week 12 for a primary endpoint visit and at Week 24 for a nominal Week 24 visit.

Follow-up period: Approximately 2 weeks after the last dose of IMP, participants will attend a follow-up visit for safety assessments. Women of childbearing potential treated with alitretinoin will attend an additional follow-up visit for a pregnancy test, 5 weeks after the last dose of alitretinoin

Refer to Section 10.5 for coronavirus disease 2019 (COVID-19) pandemic contingency plan.

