6.3 Measures to Minimise Bias: Randomisation and Blinding

Due to the different administration routes for the 2 IMPs, participants are not blinded to treatment assignment. A double-dummy design is not considered feasible since addition of the cream vehicle to alitretinoin-treated participants may increase the clinical effect in the alitretinoin arm. To ensure unbiased clinical assessments, efficacy (IGA-CHE and HECSI) will be evaluated by a blinded assessor. Each site will have at least 1 dermatologist or allergist and 1 physician to allow for both an unblinded investigator and a blinded assessor. The sponsor will ensure appropriate measures are in place to keep information about treatment assignment segregated from the blinded assessor. Such measures will include training of site personnel and participants, as well as separate systems access and source documentation.

In addition, to minimise the risk of potential bias into final analyses, a blinding maintenance plan will be implemented by the sponsor and by the CRO to maintain the integrity of the trial data for the decision making at the final analyses. The details regarding access to blinded or unblinded data by the site, CRO and sponsor staff, as well as blinding procedures, will be outlined in the blinding maintenance plan. The blinding maintenance plan will be finalised prior to the first participant first visit. Although the trial is not double-blinded, the specific treatment to be taken by a participant will be randomly assigned using interactive response technology (IRT). The site will contact the IRT prior to the start of IMP administration for each participant. The site will record the treatment assignment on the applicable eCRF, if required.

Trial treatment will be administered/dispensed at the trial visits as summarised in the SoA (Table 1-1). Returned IMP should not be re-dispensed to the participants.

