6.5.1 Retreatment Criteria

For participants who achieve an IGA-CHE score of 0 or 1 after 16 weeks of delgocitinib treatment or 12 weeks of alitretinoin treatment, it is recommended to discontinue treatment.

However, these participants must restart treatment if they relapse to an IGA-CHE score of ≥ 2 and will remain on continuous treatment until Week 24.

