7.3 Loss to Follow-Up

A participant will be considered lost to follow-up if they repeatedly fail to return for scheduled visits and are unable to be contacted by the trial site.

The following actions must be taken if a participant fails to return to the clinic for a required trial visit:

[figure not shown]
- The site must attempt to contact the participant and reschedule the missed visit as soon as possible (and within the visit window, where one is defined), counsel the participant on the importance of maintaining the assigned visit schedule, and ascertain whether the participant wishes to and/or should continue in the trial.
- In cases in which the participant is deemed lost to follow-up, the investigator or designee
 must make every effort to regain contact with the participant (where possible, 3 telephone
 calls and, if necessary, a certified letter to the participant's last known mailing address or
 local equivalent methods). These contact attempts should be documented in the participant's
 medical record/CRF.
- Should the participant continue to be unreachable, he/she will be considered to have withdrawn from the trial.

8 Trial Assessments and Procedures

Trial procedures and their timing are summarised in the SoA (Table 1-1). Protocol waivers or exemptions are not allowed.

Assessments and procedures at each trial visit should be performed in the order shown in Figure 8–1.

Figure 8–1 Sequence of Assessments

Abbreviations: HECSI=Hand Eczema Severity Index; IGA-CHE=Investigator's Global Assessment for chronic hand eczema[©]; IMP=investigational medicinal product; PRO=patient-reported outcome.

Trial participants will be under careful supervision of a principal investigator who must be a dermatologist or allergist. Investigators must be experienced in treating CHE, have documented experience and completed training in use of the assessments required by the protocol, and must be a physician.

AEs must be assessed by a physician (Section 8.3).

Immediate safety concerns should be discussed with the sponsor immediately upon occurrence or awareness to determine if the participant should continue or discontinue the IMP.

Adherence to the trial design requirements, including those specified in the SoA, is essential and required for trial conduct.

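### Section 4.1 words the blinded assessor's continue/stop/restart recommendation for alitretinoin only, which, followed literally, would disclose the arm after Week 12

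*Combined protocol and SAP*

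**What the plan says.** Section 4.1 has HECSI and IGA-CHE scored by an assessor who does not know the treatment. It then lists two recommendations that this assessor makes from those scores. The first, on discontinuing to start rescue medication, names no arm. The second reads "To continue, stop or restart treatment from Week 12 and onwards for alitretinoin (Section 6.5.1".

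Four other places bear on the same task:

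- **Section 4.1, the unblinded investigator's list:** "Decisions to continue, stop or restart the IMP from Week 16 for delgocitinib or Week 12 for alitretinoin (Section 6.5.1".
- **Section 6.5.1, which both lists cite:** for participants with an IGA-CHE score of 0 or 1 "after 16 weeks of delgocitinib treatment or 12 weeks of alitretinoin treatment, it is recommended to discontinue treatment", with restart on relapse in either arm. The assessor is not mentioned.
- **Synopsis (Section 1.1):** the unblinded investigator decides after the assessor's recommendation. No arm is named.
- **Section 6.3:** "The sponsor will ensure appropriate measures are in place to keep information about treatment assignment segregated from the blinded assessor". It adds: "Such measures will include training of site personnel and participants, as well as separate systems access and source documentation". Details of data access, "as well as blinding procedures, will be outlined in the blinding maintenance plan".

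Section 8 also fixes a sequence for each visit ("Assessments and procedures at each trial visit should be performed in the order shown in" Figure 8-1). Neither that figure nor the blinding maintenance plan is available here.

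**The concern.** Participants and investigators know the treatment, so the blinded assessor is the main protection for HECSI and IGA-CHE. Someone who does not know the arm cannot tell for whom an alitretinoin-only recommendation is due. If site staff ask for it only for alitretinoin participants, the request itself gives the arm away. Either way, an assessor who has made such a recommendation at Week 12 would score later visits knowing the treatment.

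Those later scores enter two confirmatory key secondary endpoints in the Section 9.1.1 sequence: no. 5, AUC of HECSI-90 to Week 24, and no. 7, change in HECSI to Week 24. They also enter the exploratory Week 24 results for IGA-CHE treatment success, HECSI-75 and HECSI-90.

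**Working it through.** The plan gives no figure on this point. The check is a comparison of texts, followed by a calculation of how much of endpoint 5 comes from visits after Week 12.

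**1. Scope of the recommendation, side by side**

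| Place | Who acts | Arms covered |
|---|---|---|
| Section 4.1, assessor, rescue | Blinded assessor | None named |
| Section 4.1, assessor, continue/stop/restart | Blinded assessor | Alitretinoin only |
| Section 4.1, investigator's list | Unblinded investigator | Both |
| Section 6.5.1 | Not stated | Both |
| Synopsis | Investigator, after the assessor's recommendation | None named |

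Only one row is limited to one arm, and it belongs to the person from whom Section 6.3 withholds the arm. The rescue recommendation shows that the assessor can advise without knowing the arm. The problem is therefore this one item, not the practice of assessor recommendations.

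**2. Timing**

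The recommendation is based on the efficacy assessments and starts at Week 12. The Week 12 scores therefore come before the first such recommendation. The primary endpoint and key secondary endpoints 1 and 2 (HECSI-90 and IGA-CHE success at Week 12) are not shown to be exposed. Endpoints 3, 4 and 6 (itch, pain, DLQI) are reported by participants who know their treatment in any case.

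**3. Weight of the later visits in endpoint 5**

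Inputs: HECSI visits at Weeks 0, 1, 2, 4, 8, 12, 16, 20 and 24 (Schedule of Activities); trapezoidal rule with the baseline value set to 0 (Section 9.3.6.4). Days from baseline are 0, 7, 14, 28, 56, 84, 112, 140 and 168. Each inner visit has weight (next day − previous day)/2. The first and last visits have half of their single gap.

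| Week | 0 | 1 | 2 | 4 | 8 | 12 | 16 | 20 | 24 |
|---|---|---|---|---|---|---|---|---|---|
| Weight (days) | 3.5 | 7 | 10.5 | 21 | 28 | 28 | 28 | 28 | 14 |

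- Total: 168 days. Baseline can never contribute, so 168 − 3.5 = 164.5 days are attainable.
- Weeks 16, 20 and 24: 28 + 28 + 14 = 70 days; 70/168 = 41.7%, 70/164.5 = 42.6%.
- Weeks 1 to 12: 7 + 10.5 + 21 + 28 + 28 = 94.5 days; 94.5/164.5 = 57.4%.
- Check: 70 + 94.5 = 164.5.

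For endpoint 7, the only post-baseline score used is the one at Week 24, where it is observed and no intercurrent event has occurred.

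**The case against.** The strongest reply is that the passage has a harmless reading. Its lead-in calls the assessor blinded and makes the efficacy scores the basis of the recommendation. The criteria are score thresholds: IGA-CHE 0 or 1 for stopping, and 2 or more both for possible continuation and for restart. An assessor who sees only today's score can supply all of that, and the unblinded investigator can add arm, timing and judgement of benefit.

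Much of this stands. A reader might infer that the word restart forces the assessor to know who is off drug. The documents do not support that: continue and restart share a threshold, so the current score is enough. What the harmless reading does not explain is why the item names one arm. The text does not say that the recommendation is made for everyone and then applied by arm.

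A reader might also reason from treatment status to arm. Delgocitinib runs to Week 16 whether or not the skin has cleared (Section 6.2.1.1). Participants who stop because of clearance keep attending (Section 4.2), while those who discontinue permanently do not: "they will stop attending the treatment period visits". If the protocol is followed, someone off drug at the scheduled Week 16 visit is therefore on alitretinoin. The inference is sound, but nothing gives the assessor that status, and Section 6.3 already separates systems and source documents. That Section 6.3 does not name on/off-drug status is at most a missing detail.

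Third, the blinding maintenance plan and Figure 8-1 may settle the matter. That is a fair limit on the conclusion. Section 4.1 would still need to match them, because Section 10.1.10 requires sites to follow the protocol as written.

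Finally, the 70-day share would describe any concern about visits after Week 12. Under the composite strategy, results after rescue or permanent discontinuation count as failure whatever the assessor scores, so those participant-days carry no assessor influence.

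**Conclusion.** The inconsistency is real and in the current text. One item in Section 4.1 gives the blinded assessor an arm-specific task, at odds with the Synopsis, the investigator's list in the same section, Section 6.5.1 and the segregation in Section 6.3. Followed literally, it discloses the arm. It should be corrected as an avoidable risk to HECSI and IGA-CHE scores after Week 12, and so to key secondary endpoints 5 and 7.

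A reader might go further and infer that assessors are unblinded, that the primary result is compromised, or that about 42% of endpoint 5 is biased. The documents support none of these. No unblinding is shown, the Week 12 scores precede the recommendation, and the percentages are visit weights that neither estimate nor bound a bias. Neither its size nor its direction can be derived. The risk also depends on sites acting on the literal wording and on the blinding maintenance plan not already preventing it. Endpoint 5 is tested only if the primary and the first four key secondary endpoints succeed, and endpoint 7 only after six.

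**What to change.** Remove the arm-specific wording from the assessor's task in Section 4.1, and reconcile the Synopsis, both lists in Section 4.1, Section 6.3 and Section 6.5.1. The text should say three things:

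- Any continue/stop/restart recommendation by the assessor rests on the current score alone and is recorded after HECSI and IGA-CHE, in the same form for every participant.
- The assessor is not told the arm or whether the participant is currently on treatment.
- The unblinded investigator applies the existing rules, including their arm-specific timing.

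This changes what the assessor records and what the assessor is told. It does not change when anyone stops, restarts or receives rescue, and the decision stays with the investigator. If the blinding maintenance plan already works this way, align Section 4.1 to it.

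The cost is protocol wording, a matching check of the blinding maintenance plan and retraining at the approximately 80 sites. No staff or visits are added.

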4.2 Scientific Rationale for Trial Design

This is a randomised, assessor-blinded, active-controlled, parallel-group, multi-site trial, which will be conducted in accordance with the protocol, International Council for Harmonisation of

Technical Requirements for Pharmaceuticals for Human Use (ICH) Good Clinical Practice (GCP), and applicable regulatory requirements.

Patients with hand eczema represent a heterogeneous population as hand eczema is associated with different aetiologies and morphologies. To mitigate any potential difference in trial outcome based on baseline characteristics, the trial participants will be randomised in a stratified manner. The randomisation will minimise selection bias and minimise influence of confounding factors, and the stratification will ensure a balance of the treatment groups with respect to subtype (hyperkeratotic/non-hyperkeratotic) and region.

The trial will include a maximum of 20% of participants with hyperkeratotic subtype. Based on data from the phase 2b trial and the CARPE registry (Apfelbacher et al, 2014), the proportion of patients with hyperkeratotic subtype in the CHE background population is 20%, when calculated based on the aetiology of irritant and atopic CHE prevailing over the hyperkeratotic diagnosis. As there was a clear overrepresentation of participants with hyperkeratotic subtype in previous trials with alitretinoin (Ruzicka et al, 2008; Ruzicka et al, 2004), the rationale for limiting the proportion of participants with a hyperkeratotic subtype in this trial is to ensure a representative proportion of participants with this particular subtype.

As no topical treatment is approved for moderate to severe CHE, delgocitinib cream will be compared with alitretinoin capsules. Due to the different administration routes for delgocitinib and the active comparator (alitretinoin), participants and investigators will not be blinded to treatment assignment. However, the evaluation of efficacy (IGA-CHE and HECSI) will be performed by a blinded assessor (see Section 6.3). Certain CRO and sponsor staff will also be blinded to ensure the integrity of the trial.

Participants randomised to the alitretinoin arm will not receive delgocitinib vehicle cream because the vehicle cream may influence both the physician's clinical evaluation and patient-reported outcomes (PROs). Both arms are allowed to use their normal and preferred emollient throughout the trial in line with standard care of CHE.

Two ongoing pivotal vehicle-controlled phase 3 trials (trial LP0133-1401 and trial LP0133-1402) are confirming the efficacy and evaluating the safety of delgocitinib cream 20 mg/g twice-daily for 16 weeks in patients with moderate to severe CHE (plus 36-week safety evaluation in a long-term extension trial, trial LP0133-1403). The current trial enrols patients with severe CHE only, because alitretinoin is only approved for the treatment of severe CHE.

In the 2 vehicle-controlled trials, the primary endpoint is assessed at Week 16. However, the recommended continuous treatment with alitretinoin is 12 weeks with a label recommendation to

discontinue treatment in patients who have achieved an IGA-CHE score of 0 (clear) or 1 (almost clear) after 12 weeks and earlier than 24 weeks, and with an option to restart treatment in case of worsening. To ensure comparable evaluation in the 2 arms, the primary endpoint in this trial will be assessed at Week 12. After Week 12, alitretinoin will be used as per label with a recommendation to discontinue treatment if participants achieve an IGA-CHE score of 0 (clear) or 1 (almost clear) at the investigator's discretion. Delgocitinib treatment will be continuous until Week 16 as in the pivotal phase 3 trials and based on data from the phase 2b dose ranging trial LP0133-1273. After Week 16, it will be recommended to discontinue treatment with delgocitinib if the participants achieve an IGA-CHE score of 0 (clear) or 1 (almost clear), at the investigator's discretion, with an option to restart treatment in case of worsening.

Participants who stop treatment with delgocitinib or alitretinoin because they achieve an IGA-CHE score of 0 or 1 will continue to attend the treatment period visits as planned. The protocol requires that participants who relapse (defined as an IGA-CHE score of \geq 2) after stopping treatment must restart treatment, as this is expected to mimic clinical practice.

The trial endpoints were selected to compare the efficacy of delgocitinib and alitretinoin in improving the extent and severity of CHE. Both the HECSI and the IGA-CHE will be used in this clinical trial as investigator-rated assessments of disease severity. The HECSI is an instrument used to score both the extent and the severity of the disease. The IGA-CHE is an assessment of the participant's global CHE severity at a given timepoint and is based on a 5-point scale ranging the severity of the disease from 0 (clear) to 4 (severe). The primary endpoint of the trial is change in HECSI score from baseline to Week 12.

The trial endpoints will also address the impact on health-related quality of life, work productivity, and treatment satisfaction.

AEs selected as exploratory endpoints (headache, hypertriglyceridaemia, hypercholesterolaemia, and liver toxicity) are based on the current knowledge of the safety profile of alitretinoin.

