2.3.1 Risk Assessment

Delgocitinib cream is a topically applied JAK inhibitor. Oral JAK inhibitors are associated with potential safety concerns of serious infections, all-cause mortalities, major adverse cardiovascular events, malignancies, thrombosis, lipid elevations and low blood cell counts. These risks are not considered relevant for delgocitinib cream due to the low systemic exposure observed in previous trials with topically applied delgocitinib in CHE patients.

No specific adverse drug reactions or important identified risks have been identified for delgocitinib cream during the nonclinical and clinical development to date. Nevertheless, as observed with other topical therapies, local skin reactions, such as pain (burning and stinging), sensitisation to IMP, allergic and irritant contact dermatitis, local immunosuppression, and skin infections, may occur. A detailed overview of nonclinical and clinical data on delgocitinib is available in the IB.

Table 2-1Risk Assessment

Potential Risk of Clinical Significance	Summary of Data/Rationale for Risk	Mitigation Strategy					
Delgocitinib							
Lymphocytopenia	Lymphocytopenia was observed in oral nonclinical toxicity studies and is considered a potential clinical consequence of systemic levels of delgocitinib. Lymphocytopenia is therefore considered an important potential risk for delgocitinib cream (see IB Section 5.4 and Section 7.2.2).	Haematology parameters including WBC count (with differential count) will be monitored during the trial (see Section 8.2.4).					
Local skin infection and acneiform eruptions	Potential risks that could arise from use of delgocitinib cream are local skin infection and acneiform eruptions, which have been reported in clinical trials, studying a different formulation (delgocitinib ointment) in atopic dermatitis (see IB Section 7.2.3).	Patients with clinically significant infections on the hands (exclusion criterion 5), a serious skin infection requiring parenteral antibiotics (exclusion criterion 7.b) will be excluded from the trial. During the trial, eczema herpeticum will be monitored as an AESI (see Section 8.3.6). Physical examination including whole body inspection of the skin will be performed at screening and the end of treatment and during any trial visit or unscheduled visits if necessary.					

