9.3.11.3 Clinical Laboratory Evaluation

For laboratory parameters, the absolute values as well as the changes from baseline will be summarised by visit for each treatment group.

A shift table will be produced for relevant parameters showing the categories at baseline against those at each post-baseline visit.

For participants with post-baseline values, the number of events reported up to Week 26 will be summarised. For the following laboratory abnormalities endpoints, binary estimand strategy will be applied, as described in Section 9.3.6.3:

- Increased levels of triglycerides >3.42 mmol/L (fasted state).
- Increased levels of cholesterol >7.75 mmol/L (fasted state).
- Increased levels of ALT and/or AST >3×ULN (or >3×baseline if baseline was abnormal but <2×ULN).
- Increased levels of ALP > 2.5 × ULN.
- Increased levels of bilirubin >1.5×ULN up to Week 26.

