9.5 Sample Size Determination

Approximately 510 participants will be randomly assigned to trial treatment in a 1:1 ratio, with 255 evaluable participants per treatment group. Approximately 660 participants will be screened to achieve this target.

With 510 participants randomised, the trial will provide 80% power to establish superiority of delgocitinib cream with regard to change from baseline to Week 12 in HECSI based on a 1-sided hypothesis test at a 2.5% significance level, assuming a difference in the mean change from baseline to Week 12 in HECSI of 7.5 (with a standard deviation of 30) between the 2 treatment arms (Ruzicka et al, 2008). Since there is limited published data on alitretinoin in terms of HECSI, anticipated treatment difference between delgocitinib and alitretinoin has been set using IGA scales as a surrogate endpoint (LP0133-1273 trial). Expected standard deviation is based on data observed in LP0133-1273 trial.

10 Supporting Documentation and Operational Considerations

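### All nine exploratory safety endpoints cover headache, lipid or liver harms, while lymphocytopenia, a named potential risk of delgocitinib, has no exceedance endpoint and no planned between-arm estimate

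*Combined protocol and SAP*

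**What the plan says.** Table 3-2 sets an exploratory objective of comparing the safety of the two treatments and lists nine endpoints under it. Four are AE groups: hypertriglyceridaemia, hypercholesterolaemia, headache and liver toxicity. Five are laboratory exceedances: triglycerides, cholesterol, ALT/AST, ALP and bilirubin. Section 4.2 gives the basis for the AE terms: "AEs selected as exploratory endpoints (headache, hypertriglyceridaemia, hypercholesterolaemia, and liver toxicity) are based on the current knowledge of the safety profile of alitretinoin".

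Section 9.3.11.3 applies the binary method of Section 9.3.6.3, a stratified difference in proportions, to those five laboratory exceedances and to no others. Section 9.3.11.1 plans specific AE summaries, with predefined MedDRA search terms, for the same four AE groups.

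On delgocitinib, Table 2-1 in Section 2.3.1 says: "Lymphocytopenia is therefore considered an important potential risk for delgocitinib cream". The stated mitigation is monitoring: "Haematology parameters including WBC count (with differential count) will be monitored during the trial". The analysis this leads to is in Section 9.3.11.3. Laboratory values and changes are summarised by visit and arm, and "A shift table will be produced for relevant parameters showing the categories at baseline against those at each post-baseline visit". The parameters are not named.

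Three secondary safety endpoints stand above the exploratory set: treatment-emergent AEs, treatment-emergent SAEs, and AEs leading to IMP discontinuation.

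**The concern.** A comparative safety objective should give each drug's suspected harms a comparable route into the results. Here the comparator's lipid and liver harms are counted twice, once as AEs and once by an objective laboratory threshold with a between-arm estimate. The laboratory harm that the plan itself attaches to delgocitinib has no objective count. A low lymphocyte value reaches a participant-level table by arm only if lymphocytes are treated as a relevant shift-table parameter, or if the investigator, who knows the treatment (Section 4.1), calls the value clinically significant.

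At stake is what the event-specific part of the safety comparison can show. As written, it can estimate differences for harms expected with alitretinoin, but it has no planned estimate for the laboratory harm suspected with delgocitinib.

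**Working it through.** **1. The plan's own figure.** No safety endpoint has a stated sample size or power, so the only figure to reproduce is the primary one, which fixes the number per arm. Section 9.5 gives "HECSI of 7.5 (with a standard deviation of 30) between the 2 treatment arms", a "1-sided hypothesis test at a 2.5% significance level" and 80% power.
- n per arm = 2 × (1.960 + 0.842)² × 30² / 7.5² = 2 × 7.849 × 16 = 251.2, so 252 per arm and 504 in total, against 510 stated.
- At 255 per arm, SE = 30 × √(2/255) = 2.657 and 7.5 / 2.657 = 2.823. Power = Φ(2.823 − 1.960) = 80.6% (80.4% with the noncentral t).

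The stated figure reproduces, and 255 per arm is used below.

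**2. Count of safety endpoints (Table 3-2, Section 9.3.11.3).**

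| Set | Number | Headache, lipid or liver | Neutral | Specific to a delgocitinib risk |
|---|---|---|---|---|
| Secondary | 3 | 0 | 3 | 0 |
| Exploratory | 9 | 9 | 0 | 0 |
| All | 12 | 9 | 3 | 0 |
| Laboratory exceedances with between-arm analysis (part of the nine) | 5 | 5 | 0 | 0 |

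Section 4.2 covers only the four AE terms. That the five laboratory thresholds belong to the same profile is an inference from the organ systems.

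**3. What lymphocytes receive.**
- Measurement: haematology is scheduled in both arms at screening, baseline, Weeks 4, 8, 12, 16, 20 and 24, and follow-up (Table 1-1). Lymphocytes are in the panel (Table 10-1).
- Classification: the central laboratory flags each result low, normal or high (Section 8.2.4).
- Summary: values and changes by visit. Section 9.3.1 includes median, quartiles, minimum and maximum.
- Shift table: by visit, if lymphocytes are included. It does not count participants who were low at any visit.
- AE tables: by arm, if the investigator judges the value clinically significant (Sections 8.2.4, 9.3.11.1 and 10.3.1).
- Endpoint, threshold, AE search group, AESI: none.

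**4. What an ever-low count could deliver.** The documents give no lymphocyte rates, so the rates below are assumptions. Half-width = 1.96 × √[p₁(1−p₁)/255 + p₂(1−p₂)/255], unstratified. Power is for a 2-sided 5% test.

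| Alitretinoin | Delgocitinib | 95% CI half-width | Power |
|---|---|---|---|
| 1% | 3% | 2.4 points | 36% |
| 1% | 5% | 2.9 points | 76% |
| 2% | 4% | 3.0 points | 26% |
| 2% | 7% | 3.6 points | 78% |

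The chance of at least one case among 255 on delgocitinib is 1 − (1−p)²⁵⁵: 72% at a true rate of 0.5% and 92% at 1%. Zero cases would give a 1-sided 95% upper bound of 1 − 0.05^(1/255) = 1.17%. Excluding participants low at baseline shrinks the denominator slightly. With 230 per arm, for example, the 2.9-point half-width becomes 2.94 × √(255/230) = 3.1 points.

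**The case against.** A reader might infer that every comparative safety endpoint is an alitretinoin harm and that the whole safety comparison is tilted. The documents do not support that. The three secondary endpoints are neutral and rank higher, no safety endpoint is in the testing hierarchy (Section 9.1.1), and the basis for the AE terms is disclosed. Lipid elevation is also listed as a concern with oral JAK inhibitors, although Section 2.3.1 considers it not relevant to the cream.

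A reader might also infer that delgocitinib's risks go unreported. They do not. Eczema herpeticum and deep vein thrombosis or pulmonary embolism are AESIs, tabulated by arm. Local tolerability of the cream is summarised. A clinically significant low count becomes an AE.

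Nor can it be said that falls would be invisible. Suppose 2% or 5% of an arm lost 0.8 × 10⁹/L. The mean would move by 0.016 or 0.040, against an SE of 0.5 × √(2/255) = 0.044. Those inputs are assumed, however, and the planned quartiles and minimum could still show marked falls. The point does not rest on this example.

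The lymphocyte signal comes from oral nonclinical studies, and Section 2.3.1 reports no specific adverse drug reaction for the cream. Section 9 describes itself as a summary and refers to the SAP for technical detail, so the shift-table parameters may be named there.

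All of this narrows the point without removing it. Table 2-1 still classes lymphocytopenia as an important potential risk. A minimum or a visit-level shift table is not a count of participants ever affected. AE entry depends on an unblinded judgement, and the endpoint list in Table 3-2 contains no lymphocyte item.

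**Conclusion.** The concern holds for the event-specific comparison only. Nine of nine exploratory safety endpoints and five of five compared laboratory exceedances lie in the headache, lipid and liver domains. None of the 12 safety endpoints is specific to a delgocitinib risk, and lymphocytopenia has no planned between-arm estimate. It does not follow that the overall safety assessment is biased, or that a lymphocyte effect exists or would be missed.

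The count rests on the documents. The precision figures rest on assumed rates of 1–2% and 3–7%. At those rates, power is only 26–36% for two-point differences, so the added endpoint would be descriptive and would not call for a change in sample size. This is an inexpensive improvement to reporting, and it could also help delgocitinib by putting an upper bound on the risk if no cases occur.

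**What to change.** - **Endpoint.** In Table 3-2 and Section 9.3.11.3, add: *number of participants with any post-baseline lymphocyte count flagged low by the central laboratory up to Week 26, among those not low at baseline*. Report it in both arms on the safety analysis set as a difference in proportions with 95% CI, stratified by region and subtype.
- **Data rule.** Use the observed worst post-baseline value. Do not carry over the non-response imputation of Section 9.3.6.3. It is written for efficacy, its meaning for a harm is undefined, and on one reading it would erase events.
- **Opportunity for sampling.** Table 1-1 schedules no haematology at the Week 12 primary endpoint visit or the nominal Week 24 visit for participants who stopped IMP early. Tabulate the number of post-baseline samples by arm beside the result.
- **Shift table.** Name lymphocytes among the parameters.
- **Optional.** Add grouped AE summaries by arm for skin infections and acneiform eruptions, which Table 2-1 also lists. The lesional/distant location (Section 10.3.3) is specified for delgocitinib participants only, so it cannot be used as a between-arm comparison.

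The cost is one or more extra tables from data already collected, with no new sampling. The downside for the sponsor is that delgocitinib's safety profile may look somewhat less favourable.
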